9.3 VALIDATION COHORT

Dipartimento Area Materno - Infatile

SC NEFROLOGIA E DIALISI PEDIATRICA – TRAPIANTI DI RENE – Direttore: [name]

[contact]

email: [contact]

Inclusion criteria

1. Previous clinical diagnosis of idiopathic nephrotic syndrome (nephrotic range proteinuria uPr/uCr ratio > 2mg/mg, hypoalbuminemia < 3.0 g/dl, oedema);
2. age between 1 and 18 years at onset
3. signed informed consensus

Exclusion criteria

1. Congenital or infantile nephrotic syndrome (age < 1 year old); secondary nephrotic syndrome; glomerulonephritis; autoimmune diseases; vasculitis.
2. Absence of signed informed consensus

10. Study procedure

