Medical University Gdansk	Rare Diseases Centre and Department of Biology and Medical Genetics	[name]	Biological sample processing, exome sequencing analysis
University of Istanbul	Division of Pediatric Nephrology.	[name]	Patients recruitment, biological sample processing, epigenetics analysis
Vilnius University Faculty of Medicine	Clinic of Children's Diseases	[name]	Patients recruitment and bioinformatic analysis

External services

Name	Type of service
University of Torino, [name]	EV data analysis

Dipartimento Area Materno - Infatile

SC NEFROLOGIA E DIALISI PEDIATRICA – TRAPIANTI DI RENE – Direttore: [name]

[contact]

email: [contact]

Eurofins, Italy	Novaseq 6000
MacroGen UE	Sample shipping and exome sequencing

4. Amendments

Not applicable.

5. Timelines

Stato dello studio	Pianificazione
Inizio della raccolta dati	30/10/2024
Fine della raccolta dati	30/10/2027
Report finale dello studio	30/03/2028

Dipartimento Area Materno - Infatile

SC NEFROLOGIA E DIALISI PEDIATRICA – TRAPIANTI DI RENE – Direttore: [name]

[contact]

email: [contact]

6. Rationale and background

Idiopathic nephrotic syndrome (INS) is the most common glomerular disease in children, with an annual incidence of 2-7 cases per 100,000 children. INS is characterized by proteinuria, edema, hypoalbuminemia, hyperlipidemia, and thrombotic complications (1). The disease has an extremely variable clinical behavior, and the first-line treatment is based mainly on steroids and other immunosuppressive (IS) drugs. The response to steroids guides the actual classification. Approximately 80–90% of patients with nephrotic syndrome are initially steroid sensitive (SSNS), while 10–20% will not achieve remission despite second or third-line treatments and are defined as steroid resistant (SRNS) (2). The SSNS population exhibits an uncertain clinical course, characterized by various relapses and requiring immunosuppressive treatment, prolonged into adulthood in 1/3 of patients. These treatments have major side effects and come with an increased socio-economic burden as seen all over Europe.

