There is no biomarker able to predict the INS clinical course (response to treatment and occurrence of relapses) and to tailor the treatment for most patients. INS, at least in the steroid-sensitive forms, shows an immune pathogenesis. Potential causative circulating factors have been described, however none has been unequivocally shown to be pathogenic. The recent identification of genetic risk loci associated with HLA Class II region among the most represented in SSNS patients (3) emphasizes the central role of adaptive immunity in the NS pathogenesis. From the cellular side, various experimental evidence implies that dysfunction in some populations of T lymphocytes may be related to the pathogenesis of the disease (4). Among these, a Th17/Treg imbalance has been described in patients with minimal change glomerulopathy (5). Furthermore, the remission after the use of Rituximab, a monoclonal antibody against the CD20 surface antigen, suggests that B cells may also be involved in the pathophysiology of NS (6). The role of autoantibodies as circulating permeability factors able to directly damage the glomerular barrier, leading to proteinuria in INS, has been recently explored. Antibodies against Annexin A2, actin and ATP-synthase, ubiquitin-C-terminal hydrolase L1, and CD40 antibodies were detected across both pediatric and adult INS patients in a variable percentage of INS patients highlighting the complexity of this pathology. Recently, the presence of anti-nephrin antibodies in post-transplant recurrent focal segmental glomerulosclerosis patients (7), as well as in the blood and kidney biopsies of patients with minimal change disease (8).

As shown, INS displays a multifactorial and complex pathogenesis, where immunological, genetic, and epigenetic factors are involved. There is therefore an urgent medical need to find early biomarkers to allow for a precise selection and duration of the treatment, avoiding unnecessary severe side effects, and to characterize sub-cohorts for clinical studies. Biofluid secretome can harbor promising disease biomarkers (9). These biomarkers will also favor the understanding of the pathogenesis, allowing for an alternative classification and stratification of the patients.

The PRECISE proposal aims to address unmet needs in INS children, searching for biomarkers/indicators/predictors of this rare kidney primary disease. In this context, we hypothesize

Dipartimento Area Materno - Infatile

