9.2 CONTROL GROUP

Inclusion criteria

1. Clinical diagnosis of minor congenital abnormalities of kidney and urinary tract
2. Absence of proteinuria (uPr/uCr < 0.2 mg/mg)
3. age below 18 years
4. signed informed consensus

Exclusion criteria

1. Immune-mediated diseases not associated with proteinuria (glomerulonephrities)
2. age > 18 Years

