10.1 Study visits

Population 1 (main population incident INS):

At the enrollment visit, prior informed consent the following assessments will be performed: physical examination, assessment of oedema, measurement of vital signs, blood and urine samples collection (see A. Schedule of assessments for more details). Afterwards, patients will be assessed at 6 weeks, 6 months and 12 months according to A. Following the international guidelines, at the 12 months visit patients will be clinically classified as SRNS, SDNS, or IRNS according to their medical history. Schedule of assessments: main population (incident INS).

Patient will come back to the center in case of relapse (see definitions) to perform the ‘first relapse visit’ according to A. Schedule of assessments: main population (incident INS).

Population 2 (control group):

This population will perform after informed consent only the enrollment visit, according to B. Schedule of assessments: control group.

Population 3 (validation cohort):

Patient will be enrolled after informed consent at relapse (enrolment visit). During this visit, a physical examination, assessment of oedema, measurement of vital signs and collection of blood and urine samples will be performed according to C. Schedule of assessments: validation cohort. At the remission (see definitions), patients will come back to the center to perform the remission visit according to C. Schedule of assessments: validation cohort.

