10.4 Medical history

Medical history will be recorded at enrollment visit. Investigators should document the occurrence, signs, and symptoms of the participant's preexisting conditions, including all prior significant illnesses. A detailed medical history about disease indication will be requested and will include prior surgeries, renal biopsies, hospitalizations, dialysis, transplantation, laboratory data, and extrarenal manifestations of the disease. Available disease medical history for the 3 years preceding screening will be requested.

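### The validation cohort caps age at onset but not age at sampling and does not exclude graft recipients, so it can admit patients outside the paediatric population the signature is built for.

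*Protocol*

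**What the plan says.** Section 7 sets the primary objective as a model that separates children with steroid-resistant or steroid-dependent disease from those with infrequent relapses, using data at onset. Section 6 describes the same target: "The PRECISE proposal aims to address unmet needs in INS children".

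Section 8.1 plans 110 treatment-naïve patients for discovery, 40 controls, and 200 prevalent cases as an independent validation group.

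Section 9.3 gives the validation cohort three inclusion criteria: "1. Previous clinical diagnosis of idiopathic nephrotic syndrome", the age rule "2. age between 1 and 18 years at onset", and consent. Besides absence of consent, its exclusions are congenital or infantile disease and "secondary nephrotic syndrome; glomerulonephritis; autoimmune diseases; vasculitis". It does not mention age at enrolment, time since onset, kidney function, transplantation or kidney replacement therapy.

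Section 10.1 adds the timing: "Patient will be enrolled after informed consent at relapse (enrolment visit"), with a second visit at remission. For controls, section 9.2 states "3. age below 18 years" and also excludes those over 18.

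**The concern.** The age rule in 9.3 has the same wording as the one in 9.1, but it does a different job in each cohort. In new-onset patients, age at onset is in effect age at sampling. In prevalent patients the two can be years apart, so the rule no longer limits the age at which blood and urine are taken. Nothing else in 9.3 supplies that limit, and nothing there keeps out a patient whose urine comes from a transplanted kidney.

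At stake is how the validation result can be read. Under sections 8.2 and 8.3 the signature draws on methylation, B- and T-cell subsets, and vesicle and protein profiles in urine and serum. The protocol itself treats age as relevant to such measurements, since it asks for controls of homogeneous age. In a graft recipient, urinary vesicles come from another person's kidney and the immune cells from a patient under transplant immunosuppression. If the signature performs poorly or well in such patients, it is hard to tell how much of that is due to the signature and how much to the change of population.

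**Working it through.** No figure in the plan needs reproducing for this point. The check compares the eligibility rules side by side.

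**1. What each group's criteria fix at sampling**

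| Group | Age rule | Other relevant rule | Age at sampling limited? | Transplant recipients kept out? |
|---|---|---|---|---|
| Incident (9.1) | 1 to 18 years at onset | No earlier treatment for the disease | Yes, in effect | Yes, in effect, where the graft would be for this disease |
| Controls (9.2) | Below 18 years; over 18 excluded | Minor urinary tract anomaly, no proteinuria | Yes, explicitly | Not stated |
| Validation (9.3) | 1 to 18 years at onset | Past diagnosis; enrolled at relapse | No | No |

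Only the validation row has no limit on age at sampling. Section 9.2 shows that the protocol caps current age where it intends to.

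**2. Test case for age.** Onset at 8 and relapse at 25. Past diagnosis: met. Onset between 1 and 18: met (8). Consent: can be given. Exclusions: none applies. The patient is eligible 25 − 8 = 17 years after onset.

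**3. Test case for a graft.** A child with onset after age 1, later transplanted, with proteinuria returning in the graft. The inclusion criteria in 9.3 are met and no exclusion applies. Whether this counts as a relapse depends on definitions to which section 10.1 refers and which are not in the text available here. Section 9.3 itself does not keep the patient out.

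**4. Do other sections close the gap?**
- Section 10.4 lists "prior surgeries, renal biopsies, hospitalizations, dialysis, transplantation, laboratory data" among the history items. These are recorded, not used for eligibility.
- Section 18.1 lets patients who have reached 18 sign for themselves. This sets no upper age limit.
- Section 10.1 requires a relapse and then a remission visit, and Schedule C takes urine at both. This restricts disease activity and, in practice, makes entry on maintenance dialysis unlikely. It does not restrict age or graft status.
- Section 17 promises adjustment for confounders where possible. That could cover age if enough patients overlap in age; it cannot undo a change of organ.

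**5. Size.** The share of such patients is not given. 1% of 200 = 2 patients. Purely as an assumption, 5% would be 0.05 × 200 = 10 patients and 20% would be 0.20 × 200 = 40. Nothing in the document supports a particular value, and at paediatric centres the share is probably small.

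**The case against.** The best defence is context. The sponsor's unit is a paediatric nephrology department, partners named in the protocol include a paediatric nephrology division and a children's clinic, and the consent text is written mainly for parents. Few adults are likely to be enrolled. This stands as an argument about frequency. It is not an eligibility rule, and it does not apply to transplanted children, who are seen in paediatric units; the sponsor's own unit includes dialysis and kidney transplantation.

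Three stronger readings are tempting, and the document does not support them.

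- A reader might infer that dialysis patients enter as readily as adults. Enrolment at relapse, a return visit at remission and urine sampling at both largely screen them out.
- A reader might take "prolonged into adulthood in 1/3 of patients" (section 6) to mean that about a third of the validation cohort could be adult. That figure describes how long treatment lasts in steroid-sensitive disease. It says nothing about who attends the recruiting centres or about transplantation. Likewise, the history list in 10.4 is generic and also applies to untreated incident patients, so it does not show that graft recipients are expected.
- A reader might conclude that these patients would gather in the steroid-resistant or steroid-dependent class and so bias the contrast between classes. That is plausible but not shown, and a design that requires remission after relapse works against entry of patients who never remit.

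**Conclusion.** The point holds in a limited form. As written, section 9.3 admits patients over 18 and patients with a kidney graft to the validation of a signature built in children with new-onset disease. No other section shown removes them. The likely explanation is that a criterion suited to incident patients was carried over to prevalent ones.

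The size is unknown and probably small. The 10 to 40 patients shown above rest entirely on an assumed share of 5% to 20%, and the upper end is hard to believe at mainly paediatric centres. A reader might infer that validation would tell us nothing about the paediatric signature. That goes too far: a minority of such samples would make the result harder to interpret, not worthless. Contamination of the cohort is not shown either; what is shown is that the rule allows it. The correction is worth making because it is cheap and brings the validation set into line with the stated target population.

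**What to change.** In section 9.3, keep the onset criterion and add two lines:

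- an inclusion criterion limiting age at enrolment to the range used for the incident cohort, 1 to 18 years;
- an exclusion for patients who have a kidney transplant or are on maintenance kidney replacement therapy at enrolment. It should not extend to past temporary dialysis in a child who still has native kidneys, since that child belongs to the target population.

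Alternatively, leave enrolment unchanged, define the validation analysis set without these patients, and report them separately. This also deals with anyone already enrolled under the present wording. The needed data are already planned: age under section 10.3 and transplantation under section 10.4. Because 10.4 asks for disease history over the preceding 3 years, graft status at sampling should be recorded whatever the date of transplant.

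The cost is a short amendment with ethics approval, as section 18 requires, and a slightly smaller validation set or recruitment pool. Under the second option no recruited patient is lost from the study, only from the main validation analysis.

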10.1 Study visits

Population 1 (main population incident INS):

At the enrollment visit, prior informed consent the following assessments will be performed: physical examination, assessment of oedema, measurement of vital signs, blood and urine samples collection (see A. Schedule of assessments for more details). Afterwards, patients will be assessed at 6 weeks, 6 months and 12 months according to A. Following the international guidelines, at the 12 months visit patients will be clinically classified as SRNS, SDNS, or IRNS according to their medical history. Schedule of assessments: main population (incident INS).

Patient will come back to the center in case of relapse (see definitions) to perform the ‘first relapse visit’ according to A. Schedule of assessments: main population (incident INS).

Population 2 (control group):

This population will perform after informed consent only the enrollment visit, according to B. Schedule of assessments: control group.

Population 3 (validation cohort):

Patient will be enrolled after informed consent at relapse (enrolment visit). During this visit, a physical examination, assessment of oedema, measurement of vital signs and collection of blood and urine samples will be performed according to C. Schedule of assessments: validation cohort. At the remission (see definitions), patients will come back to the center to perform the remission visit according to C. Schedule of assessments: validation cohort.

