Appendix 1. List of recruiting centers.

Dipartimento Area Materno - Infatile

SC NEFROLOGIA E DIALISI PEDIATRICA – TRAPIANTI DI RENE – Direttore: [name]

[contact]

email: [contact]

1. Schedule of assessments

A. Schedule of assessments: main population (incident INS)

	Enrolment (Onset)	6-weeks visit (End of metil- prednisolone pulses*)	6-months visit	12-months visit	First relapse
Informed consent	x				
Inclusion/exclusion criteria	x				
Demographic data	x				
Physical examination	x	x	x	x	x
Assessment of oedema	x	x		x	x
Medical history	x			x	
Vitals sign ¹	x	x	x	x	x
Clinical blood sample ²	x	x	x	x	x
Clinical urine sample ³	x	x	x	x	x
Blood for genetic analysis	x				
Blood for mononuclear cells analysis	x	x		x	x
Urine for molecular analysis	x	x	x	x	x
Serum for molecular analysis	x	x	x	x	x

¹ Height, weight, blood pressure

² BUN, sCr, albumin, Na, K, total cholesterol, IgG, triglycerides, (local laboratory) serum complement C3 (local laboratory, only at enrolment)

Dipartimento Area Materno - Infatile

SC NEFROLOGIA E DIALISI PEDIATRICA – TRAPIANTI DI RENE – Direttore: [name]

[contact]

email: [contact]

³ Urine protein/creatinine ratio, urinalysis (local laboratory)

* Only in patients not achieving remission at week 4

B. Schedule of assessments: control group

	Enrolment
Informed consent	x
Inclusion/exclusion criteria	x
Demographic data	x
Physical examination	x
Vitals sign ¹	x
Clinical blood sample ²	x
Clinical urine sample ³	x
Blood for PBMC extraction	x
Urine	x
Serum	x

¹ Height, weight, blood pressure

² BUN, sCr, albumin, Na, K, total cholesterol, triglycerides, IgG, IgM, IgA (at local site)

³ urine protein/creatinine ratio, urinalysis (at local site)

Dipartimento Area Materno - Infatile

SC NEFROLOGIA E DIALISI PEDIATRICA – TRAPIANTI DI RENE – Direttore: [name]

[contact]

email: [contact]

C. Schedule of assessments: validation cohort (prevalent INS)

	Enrolment (Relapse)	Remission
Informed consent	x	
Inclusion/exclusion criteria	x	
Demographic data	x	
Physical examination	x	x
Assessment of oedema	x	x
Medical history	x	
Vitals sign ¹	x	x
Clinical blood sample ²	x	x
Clinical urine sample ³	x	x
Blood for PBMC extraction	x	x
Urine	x	x
Serum	x	x

¹ Height, weight, blood pressure

² BUN, sCr, albumin, Na, K, total cholesterol, triglycerides, IgG, IgM, IgA (at local site)

³ urine protein/creatinine ratio, urinalysis (at local site)

Dipartimento Area Materno - Infatile

SC NEFROLOGIA E DIALISI PEDIATRICA – TRAPIANTI DI RENE – Direttore: [name]

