8.2. Primary endpoint

To describe different molecular signatures (characteristics), predictive of the progression of INS, which would be able to discriminate among SRNS/SDNS and IRNS groups, based on genetic/epigenetic background, immune status, and vesicular proteome/transcriptomic profile.

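### The validation cohort is entered only at relapse, so steroid-resistant children who have never remitted are eligible under 9.3 but have no enrolment visit

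*Protocol*

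**What the plan says.** - **Eligibility (Protocol 9.3).** The disease criterion is "Previous clinical diagnosis of idiopathic nephrotic syndrome (nephrotic range proteinuria uPr/uCr ratio > 2mg/mg, hypoalbuminemia < 3.0 g/dl, oedema". The other inclusion criteria are age at onset and consent. Relapse, remission and steroid response are not mentioned.
- **Entry (Protocol 10.1, Population 3).** "Patient will be enrolled after informed consent at relapse (enrolment visit". The only later visit is described as "At the remission (see definitions), patients will come back to the center to perform the remission visit".
- **Schedule C (Protocol Section 1).** The validation schedule has two columns, "Enrolment (Relapse") and Remission.
- **Description of SRNS (Protocol Section 6).** These are the 10-20% of patients who "will not achieve remission despite second or third-line treatments and are defined as steroid resistant (SRNS").
- **What the signature must do (Protocol 8.2).** It should "discriminate among SRNS/SDNS and IRNS groups". The primary objective in Section 7 pools SRNS and SDNS in the same way.
- **Size (Protocol 8.1).** The validation phase uses 200 prevalent cases, independent of the 110 incident ones.

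**The concern.** A relapse presupposes an earlier remission. A child whose disease has persisted since onset meets every criterion in 9.3 but reaches no visit at which 10.1 or Schedule C would enrol the child. A site cannot tell from the text whether to recruit such a child, or when to take the sample.

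The children affected belong to one component of the class that the primary objective sets against IRNS. If they are missing, the independent check of the signature is in practice a check among children who have remitted at least once. A result reported as validation of SRNS/SDNS versus IRNS would then claim more than the sample supports. No analysis can repair this later, because the children were never sampled.

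**Working it through.** **Step 1: the plan's own total.** Discovery 110 + validation 200 = 310 INS patients, which agrees with Protocol 8.1. Section 13 gives no alpha, power or effect size, so there is no power figure to reproduce.

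**Step 2: the path of a never-remitting child.**

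| Place | Condition | Never-remitting SRNS child |
|---|---|---|
| 9.3 | Previous INS diagnosis, age at onset, consent | Admitted |
| 10.1 and Schedule C, entry | A relapse | No such event |
| 10.1 and Schedule C, second visit | A remission | No such event |

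The entry condition is what keeps the child out. The second visit only means that there would be no second sample.

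**Step 3: SRNS expected without the relapse restriction.** Let p be the SRNS share, 0.10 to 0.20 (Section 6). Assume that the prevalent mix equals this share.

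- 200 × 0.10 = 20
- 200 × 0.20 = 40

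For comparison, the discovery cohort would hold 110 × 0.10 = 11 to 110 × 0.20 = 22.

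**Step 4: SRNS expected with entry only at relapse.** Let s be the share of SRNS children who remit at some time and later relapse. The protocol does not give s, so a range is shown. If all children who can relapse are equally likely to be enrolled, the expected number is

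n = 200 × p × s / ((1 − p) + p × s)

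| s (assumed) | p = 0.10 | p = 0.20 |
|---|---|---|
| 0 (Section 6 read literally) | 0 | 0 |
| 0.25 | 5 / 0.925 = 5.4 | 10 / 0.85 = 11.8 |
| 0.50 | 10 / 0.95 = 10.5 | 20 / 0.90 = 22.2 |
| 0.75 | 15 / 0.975 = 15.4 | 30 / 0.95 = 31.6 |

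For s between 0.25 and 0.75 the range is therefore about 5 to 32 of 200. In every row the children counted are those who did remit. The number who have never remitted is 0 throughout, if 10.1 is followed as written.

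**The case against.** **Section 6 is background, not a classification rule.** Section 10.1 classifies incident patients at 12 months by international guidelines and medical history. Schedule A ties the 6-week visit to patients not in remission at week 4, which points to early steroid response. If SRNS means early non-response, some SRNS children remit later, relapse and can enter. This stands, and it is why Step 4 gives a range. A reader might infer that no SRNS child can enter and that the SRNS component cannot be validated at all. The documents support that only at s = 0.

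**The definitions are not visible.** Section 10.1 refers to definitions of relapse and remission that are not in the text available for review. Their absence is not held against the plan, but they could change who counts as relapsing.

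**The remission visit is not an entry condition.** A reader might take it as a second barrier. The wording has remission trigger the visit, so a child who does not remit afterwards loses the second sample and is not excluded.

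**Eligibility and timing are different matters.** Section 9.3 says who may join; 10.1 and Schedule C say when. For children who relapse the two are compatible. They part company only for children with persistent disease, and there the objection gives no answer.

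**The study is exploratory and has another evaluation route.** Section 13 disclaims inference for the primary endpoint, Section 17 calls the study a pilot, and Section 15.1 plans evaluation in public data. SDNS versus IRNS also remains testable in the 200. All of this limits the consequence. The SRNS content of the public data is not stated, however, so that step cannot be assumed to fill the gap.

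**Class mix.** A reader might add that entry at relapse weights the cohort towards frequent relapsers by a known amount. The protocol gives neither relapse rates by class nor a target mix, so no figure can be put on this.

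**Conclusion.** The concern holds in a limited form. As written, 10.1 and Schedule C give no entry point to SRNS children who have never remitted, although 9.3 admits them. The SRNS component of the signature would be checked in the study's own validation cohort on few, possibly no, never-remitting cases.

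In numbers, 20-40 SRNS children of 200 would be expected without the relapse restriction. With it, the count is 0 if no SRNS child ever remits and about 5-32 if 25-75% remit later and relapse. These figures assume that the prevalent mix matches the share in Section 6 and that children able to relapse are equally likely to be enrolled; the 25-75% range is itself an assumption.

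The documents do not show that every SRNS child is excluded, that validation as a whole fails, or that the SDNS-versus-IRNS contrast is affected.

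**What to change.** Reconcile 9.3, 10.1 and Schedule C:

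1. State in 9.3 the disease state in which validation patients are sampled.
2. Add to 10.1 and Schedule C an enrolment and sampling point for children with persistent nephrotic disease (SRNS), alongside relapse.
3. State that the remission sample is taken only where remission occurs.
4. Report validation performance separately for SRNS, SDNS and IRNS, so that the number behind each class is visible.

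If persistent disease is not to be sampled, write the relapse condition into 9.3 and limit the validation claim to children who have relapsed after remission.

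The cost is a short amendment to three places. The total of 200 need not change. Non-remitting children will have one sample and not two, so they cannot contribute to comparisons of relapse with remission. The change concerns eligibility and sampling only and leaves clinical care as it is.
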